- **Walking Speed:** We will assess SSWS and fastest comfortable walking speed in meters per second over a 16 foot GAITRite walkway. Mean SSWS for individuals post-stroke has been established at 0.84m/s,⁵¹ with excellent test-retest reliability (ICC=0.95 to 0.99) and interrater/intrarater reliability (0.87 to 0.88).^{3,52} Minimally Clinically Important Difference (MCID) for SSWS for stroke survivors of 0.16 m/s⁵³ allows for the clinician to set meaningful walking speed goals, while providing a classification for researchers via cut off scores: <0.4 m/s representing likely limited household ambulators, 0.4-0.8 as limited community ambulatory profile, and >0.8 m/s as community ambulators.³
- **6-Minute Walk Test (6MWT):** Timed walking tests are primarily a measure of functional capacity.⁵⁴ The 6MWT tests populations who present with little functional walking capacity and is validated against the Rivermead Mobility Index ($r=0.75$) and 10-meter walk time ($r=-0.61$).⁵⁵ The 6MWT has a high intra- and interrater reliability (ICCs = 0.82-0.95).⁵⁶ The Minimal Detectable Change (MDC) for individuals with chronic stroke is 120 feet⁵⁷ and the MCID is 113 feet.⁵⁸
- **Functional Gait Assessment (FGA):** The FGA is modified from the Dynamic Gait Index and includes 10 items to assess dynamic balance stability during gait. Each item is scored on a 4-point scale from 0 (poor) to 3 (excellent) with a maximum score of 30. The MDC is 4.2 points,⁵⁹ A score 22 or below out of 30 is predictive of falls in older adults (sensitivity and specificity each 85%).⁶⁰
- **Fugl-Meyer Assessment of Motor Function:** We will utilize the lower extremity (LE FM Assessment) portion of the assessment to characterize our participant sample. The LE FM Assessment is a measure of motor recovery post-stroke and includes measures of reflex, motor control, and coordination with a total score of 34. We will also evaluate separately the 22-point motor sub-score as well as the LE sensory portion.⁶¹

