5.0 Inclusion and Exclusion Criteria/ Study Population

Subjects: We will recruit 72 individuals post-stroke, specifically targeting Veterans, with persistent motoric disability following a clinical diagnosis of stroke, the most recent no less than six months prior to enrollment. Individuals must present with unresolved propulsion asymmetry ($Pp \leq 0.47$ or ≥ 0.53). Subjects will be aged 25 to 75 years to control for the effects of advanced age on the ability to maintain the effects of motor adaptation training.⁶⁶ Participants may be of either gender and will be of diverse ethnic background representing the community. We will also perform a battery of clinical assessments to evaluate degree of function and disability.

Inclusion criteria: 1) 25-75 years of age, 2) stroke \geq 6 months, 3) residual paresis in the lower extremity (Fugl-Meyer LE motor score <34), 4) ability to walk without assistance at speeds ranging from 0.2 – 1.0 m/s (with a support harness for biomechanical testing); 5) $Pp \leq 0.47$ or ≥ 0.53 ; 6) Ability to walk on a treadmill without orthotic or assistive device using overhead harness system; 7) provision of informed consent, and 8) written approval from the primary physician (see attached sample of Medical Approval Cover Letter).

Exclusion criteria will be: 1) history of congestive heart failure, unstable cardiac arrhythmias, hypertrophic cardiomyopathy, severe aortic stenosis, angina or dyspnea at rest or during ADLs; 2) History of COPD or oxygen dependence; 3) Pre-existing neurological disorders or dementia; 3) History of major head trauma; 5) Legal blindness or severe visual impairment; 6) Severe arthritis or other problems that limit passive ROM; 7) History of DVT or pulmonary embolism within 6 months; or 8) Severe hypertension with systolic >200 mmHg and diastolic >110 mmHg at rest.

Statement of Inclusion of Women and Minorities in Research: This research will include women and minorities to the extent reflected by composition of the population in Charleston, SC and its surrounding areas. There are no exclusion or inclusion criteria which would exclude or preclude women or minorities from participating in this study.

Targeted/Planned Enrollment Table

TARGETED/PLANNED ENROLLMENT: Number of Subjects			
Ethnic Category	Sex/Gender		
	Females	Males	Total
Hispanic or Latino	5	5	10
Not Hispanic or Latino	31	31	62
Ethnic Category: Total of All Subjects *	36	36	72
Racial Categories			
American Indian/Alaska Native	0	0	0

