10.0 Study Design / Methods

This proposal seeks to develop a theory-based clinical decision-making framework for the training of walking recovery after stroke based on how different biomechanical patterns of walking illustrate distinct motor control deficits. 72 individuals with unresolved propulsion asymmetry after chronic stroke (greater than six months post-stroke, so additional natural recovery is not expected) will be evaluated to determine their baseline level of Pp: low Pp (≤ 0.47) and high Pp (≥ 0.53) (0.47 to 0.53, equal to 3 standard deviations around the mean for healthy controls). Individuals will be randomly assigned to one of three intervention groups (INCLINE, DECLINE, or CONTROL training), and we will recruit into each training group an equal number of 10 individuals with low or high Pp (Figure 6). Each participant in INCLINE training will walk four 5-minute bouts at the highest speed they can tolerate for 5 minutes (up to SSWS and at least 50% of SSWS) on a 10% up-sloped treadmill followed by 6 minutes of level overground walking at the pace that they can maintain (breaks are allowed as necessary while the clock continues to run). INCLINE training will focus on increasing force production and promoting increased and symmetrical hip extension. Those in DECLINE training will also walk with the same number of bouts, intensity, and overground walking as INCLINE on a 10% down-sloped treadmill, limiting hip extension, and promoting effective stance to swing transitions through increased knee flexion and eccentric control of the knee. During the 6-minute walk, each participant will focus on specific gait details targeted in the INCLINE/DECLINE trials (e.g. increased hip extension, increase paretic leg loading, or improved stance to swing transition). CONTROL participants will walk four 5-minute bouts at their SSWS on a flat treadmill followed by 6 minutes of level overground walking at the SSWS, controlling for equal time of walking activity. Placement into the INCLINE, DECLINE, or CONTROL training groups will be randomized based on a computerized randomization by the study statistician. Each individual will complete 12 sessions (three times a week for four weeks). Clinical and biomechanical outcome measures will be collected pre- and post-training and after a one-month follow-up period. In addition, we will collect a battery of clinical outcome measures before and after training. Spatiotemporal variables (including SSWS) will be collected before and after each session. All clinical and biomechanical assessments will be conducted by an evaluator blinded to training group allocation.

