Sample Size Determination and Statistical Approach: A total of 72 individuals post-stroke will be recruited for this study. We are assuming an attrition rate of 20% resulting in a final sample size of 60 for statistical analyses, ideally 10 in each combination of baseline group (low and high Pp) and intervention (INCLINE, DECLINE, and CONTROL training). 10% is consistent with attrition rates from previous trials of locomotor rehabilitation conducted by our group,⁴³ but we have chosen a more conservative rate of 20% based on the novelty and intensity of the intervention. There will be two strata of 30 individuals each with baseline low Pp and high Pp, respectively. From those strata, using block randomization, the subjects will be equally randomized into the INCLINE, DECLINE, and CONTROL training (10 in each training cell). The power analysis was based on our pilot training data for INCLINE and DECLINE combined compared to CONTROL. For the power analysis, we used a repeated measures model with an AR(1) correlation value of 0.45 which we obtained from the pilot data. With an average standard deviation of 0.35 (also obtained from the pilot data) and 80% power, with 10 subjects per group we will be able to detect a difference of at least 0.20 between the intervention groups and CONTROL group. A log transformation was applied to achieve normality. Also, we will longitudinally evaluate speed at each session. We will therefore conduct a repeated measures 2-way ANOVA and test the relevant hypotheses using contrasts in a Bonferroni post-hoc analysis. We will include an adjustment for baseline Pp group, intervention group, time, and their interactions. Depending on the within subject correlation across time (which we anticipate to be high) this could also provide additional power. Therefore, in a secondary analysis we will be able to examine several covariates, including the sub-types mentioned above. For each Aim, each variable will be assessed utilizing a repeated measures analysis of variance (baseline Pp, group and time) to evaluate the interaction between baseline Pp, group and time as well as the main effects of treatment for each group and group assignment at each time point. Since pilot data required a log transformation of SSWS, we will assess the final SSWS outcome for normality and perform a transformation if necessary. All power estimates were conducted by a biostatistician ([name]) using PASS 2008 (NCSS, Kaysville, Utah). Spaghetti plots and descriptive statistics regarding HR, BP, and RPE responses to INCLINE and DECLINE training will be reported prior to formal analyses. Patterns of attrition between the 2 groups will also be compared.

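### Aims 1 and 2: using each participant's own pre-training value as a covariate is a cheap precision gain, of a size the documents do not fix

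*Combined protocol and SAP*

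**What the plan says.** Section 11.0 gives the model terms twice. The general statement is "We will include an adjustment for baseline Pp group, intervention group, time, and their interactions". For each Aim, a repeated-measures ANOVA is then to be used "to evaluate the interaction between baseline Pp, group and time", together with effects of group at each time point. Other covariates are deferred: "in a secondary analysis we will be able to examine several covariates". The same section says that SSWS will also be evaluated longitudinally at every session.

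The baseline values exist for everyone. Section 10.0 states: "Clinical and biomechanical outcome measures will be collected pre- and post-training and after a one-month follow-up period".

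On correlation, Section 11.0 says "we used a repeated measures model with an AR(1) correlation value of 0.45" without giving the time lag, and elsewhere refers to "within subject correlation across time (which we anticipate to be high". Section 4.0 describes SSWS as measured "with excellent test-retest reliability (ICC=0.95 to 0.99". No reliability figure or SD is given for |0.5 − Pp|.

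**The concern.** The Pp stratum does not stand in for a participant's own starting value. It records the direction of the propulsion asymmetry, not its size, and says nothing about speed. Section 5.0 requires "ability to walk without assistance at speeds ranging from" 0.2 to 1.0 m/s, so starting speeds can differ widely within a stratum.

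If the pre-training visit is a level of time, the group-by-time contrast compares changes from baseline. The comparison of groups at a single time point does not use baseline at all. Both are valid under randomization. In large samples, neither is more precise than a comparison adjusted for baseline. Personalized v non-personalized and personalized v CONTROL are each about 20 v 20, so precision is scarce and the data that would improve it are already collected.

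**Working it through.** **Inputs.** From Section 11.0: SD 0.35 (raw or log scale not clear), AR(1) correlation 0.45 (lag not stated), difference 0.20, 80% power, 60 analysed in six cells of 10. Pooling the two strata gives 20 personalized, 20 non-personalized and 20 CONTROL. Assumed: two-sided 0.05, no Bonferroni division in the illustrations, and equal pre- and post-training variances unless stated. r is the correlation between a participant's baseline and post-training values.

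**The plan's own figure.** Take 10 v 10 on the average of 12 measurements, one per session. The AR(1) variance factor is [12 + 2Σ(12−k)0.45^k]/144 = 0.199, and SE = 0.35 × √0.199 × √(2/10) = 0.0698. The detectable difference is 2.802 × 0.0698 = 0.196, with 81.7% power for 0.20. A three-visit average with 40 v 20 (INCLINE and DECLINE pooled) also comes close: 78.3% and 0.204. With 10 v 10 over three visits, power is 39.0%. The stated figure therefore does not settle which lag the 0.45 refers to.

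**Large-sample variance per participant, in SD² units.** Post-training value alone: 1. Change: 2(1−r). Baseline-adjusted: 1−r². The saving is (1−r)/2 against change and r² against the post value alone.

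**Cost of estimating the slope.** Six cells of 10 leave 54 within-cell degrees of freedom, so the adjusted contrast is inflated on average by 1 + 1/(54−2) = 53/52 = 1.019. The net saving against change is 1 − 1.019(1+r)/2.

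| r | Saving v post alone (large sample) | Saving v change (large sample) | Saving v change (six cells of 10) |
|---|---|---|---|
| 0.45 | 20% | 27.5% | 26% |
| 0.7 | 49% | 15% | 13% |
| 0.9 | 81% | 5% | 3% |
| 0.95 | 90% | 2.5% | 0.6% |
| 0.99 | 98% | 0.5% | −1.4% |

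The net saving against change is zero at r = 51/53 = 0.96. At r = 0 there is a loss of 1.9% against the post value alone.

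**Check by simulation** (six cells of 10, 20 v 20, 6,000 runs). The SD of the estimate, change v adjusted, was 0.1154 v 0.0989 at r = 0.45, 0.0860 v 0.0801 at 0.7, and 0.0496 v 0.0488 at 0.9. Squaring the ratios gives savings of about 26%, 13% and 3%. Power for 0.20 was 39.5% v 49.8%, 62.6% v 68.6%, and 97.7% v 98.2%. Type I error was about 5% for both methods.

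**Detectable difference, Aim 1** (illustrative, large-sample): 2.802 × 0.35 × √v × √(2/20) = 0.310√v. Change v adjusted: 0.325 v 0.277 (r = 0.45), 0.240 v 0.221 (0.7), 0.139 v 0.135 (0.9). For Aim 2 only SD units are possible: 0.93 v 0.79, 0.69 v 0.63, 0.40 v 0.39.

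**Unequal variances.** Eligibility truncates baseline but not later values. With k = post SD / baseline SD, the large-sample saving against change is (1−rk)²/(1+k²−2rk). At k = 1.25 this is 13%, 2% and 5% at r = 0.45, 0.7 and 0.9, and zero at r = 0.8, where the slope cost makes it about −2%. At k = 0.8 it is 45%, 37% and 39%.

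**If 0.45 is session to session.** AR(1) then implies a baseline-to-post correlation of about 0.45^12, effectively zero. At the post-training visit there is nothing to gain over the post value alone, though change would have about twice the adjusted variance. For the 12-session average, the covariance with baseline is Σ0.45^k/12 = 0.068. The factor falls from 0.199 to 0.199 − 0.068² = 0.194, a saving of about 2%, which the slope cost nearly cancels.

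**The case against.** The strongest reply is that the planned analysis is valid and already uses baseline. With the pre-training visit as a level of time, baseline is a response in the model. The plan expects high correlation, and at r = 0.9 adjustment barely improves on change. Over much of the cited test-retest range of 0.95 to 0.99, an approximate ceiling for r, the net benefit is nil or slightly negative. For Aim 1 the plan also has a session-by-session SSWS series, and a model of the two later visits alone would drop it. Finally, the per-Aim sentence lists baseline Pp rather than Pp group. Read as a continuous value, it would carry some of the Aim 2 baseline information.

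Most of this stands and limits the point. The session series must be kept, and the gain over change may be small. The continuous reading of baseline Pp is possible, but the surrounding text treats it as the low/high group, and on either reading it does not supply baseline SSWS.

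The reply does not remove the point. The plan also lists group effects at each time point, which make no use of baseline, and it does not say which contrast is the test. Change is the weak choice when r is low; the single-visit comparison is the weak choice when r is high. Baseline adjustment is close to the better of the two, or better, at any r.

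**Conclusion.** This is a cheap improvement, not an error in the plan. The own-baseline value is not used as a covariate for Aims 1 and 2. At visit level with equal variances, using it would cut the variance of the change contrast by about 26% at r = 0.45, 13% at 0.7 and 3% at 0.9, with nothing gained near 0.96 and a loss of about 1% at 0.99. The size rests on r, which the documents leave open between a pilot 0.45 of unstated lag and an unquantified high value. For |0.5 − Pp| they give nothing.

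A reader might infer more, in three ways that the documents do not support:

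- **That the plan ignores baseline, or is biased.** On the natural reading baseline is a level of time, and the change comparison is valid with its Type I error intact.
- **That adjustment can only help.** That is a large-sample statement; with six cells of 10 the slope costs about 2% of variance.
- **That it secures 80% power.** At r = 0.45 a 20 v 20 post-training contrast stays near 50% for a difference of 0.20. Reaching 80% needs 1−r² = (0.20/0.310)² = 0.416, or r of about 0.76.

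Aim 3's responder rate is binary, has no baseline value, and is outside this point.

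**What to change.** For the visit-level contrasts in Aims 1 and 2, take the pre-training value out of the response. Model the post-training and one-month values with Pp stratum, intervention, time and their interactions, and add the baseline value of the same outcome and its interaction with time. Put baseline on the same scale as the outcome (logged if the outcome is logged). Baseline must leave the response: with baseline and baseline-by-time as covariates, a pre-training response would have a residual of exactly zero and the covariance would be singular. An equivalent option keeps baseline as a response and constrains its means to be equal across arms within each stratum.

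The baseline-by-time term is needed. Under visit-to-visit AR(1) of 0.45, a single common slope would be 0.345 instead of 0.45 at post-training, leaving about 23% of the shift from a chance imbalance uncorrected.

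Keep the session-by-session SSWS analysis, with pre-training SSWS as a covariate there too, and keep the Bonferroni contrasts. State that the visit-level model assumes data missing at random, and that a participant with neither later value does not contribute when baseline is a covariate. Fix the wording before group assignments are released for analysis, so that adjustment is not chosen from the open list of secondary covariates.

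Cost: SAP text and one or two degrees of freedom, with no new data, visits or participants. The downside is little or no gain over change if r is very high.

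### The stated 0.20 detectable difference and the remark that high correlation adds power belong to different contrasts, and at AR(1) 0.45 the 0.20 does not describe Aim 1's improvement in SSWS

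*Combined protocol and SAP*

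**What the plan says.** The power statement is in Section 11.0 (Data Management), in the paragraph on sample size determination and statistical approach.

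- Comparison: "The power analysis was based on our pilot training data for INCLINE and DECLINE combined compared to CONTROL".
- Correlation: "we used a repeated measures model with an AR(1) correlation value of 0.45 which we obtained from the pilot data".
- SD and power: "With an average standard deviation of 0.35 (also obtained from the pilot data) and 80% power".
- Result: "with 10 subjects per group we will be able to detect a difference of at least 0.20 between the intervention groups and CONTROL group".
- Scale: a log transformation is mentioned straight after the result, without saying whether 0.20 and 0.35 are log units.

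The paragraph then turns to following speed at every session with a repeated measures ANOVA that includes Pp group, intervention, time and their interactions. It adds: "Depending on the within subject correlation across time (which we anticipate to be high) this could also provide additional power". The next sentence draws a consequence: "Therefore, in a secondary analysis we will be able to examine several covariates, including the sub-types mentioned above".

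The power text states no alpha, sidedness, number of readings or type of contrast (average level, change, or group by time). Elsewhere, Aim 1 (Section 1.0) is about improved SSWS. Section 10.0 sets 12 sessions and three main assessments (before training, after training, and at one month). Section 4.0 cites a test-retest ICC of 0.95 to 0.99 for SSWS.

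**The concern.** One paragraph uses a within-person correlation of 0.45 for its calculation and then expects that correlation to be high. The two statements are not reconciled, and the choice matters because correlation acts in opposite directions on the two quantities that a repeated measures model can compare. If groups are compared on average level over the readings, highly correlated readings repeat the same information and power falls. If they are compared on change from baseline, or on baseline-adjusted speed, high correlation removes differences between people and power rises.

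A reader needs to know which quantity the 0.20 refers to. If it is an average level, it is not the improvement that Aim 1 tests, and the hoped-for extra power cannot be added to it. The covariate and sub-type analyses are then justified by a gain that the stated calculation does not deliver.

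**Working it through.** **Inputs from Section 11.0.** SD 0.35; AR(1) correlation 0.45; power 80%; difference 0.20; 10 per group. Pooling INCLINE and DECLINE over both Pp strata gives 40 vs 20 of the 60 analysed.

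**Assumed, because not stated.** Two-sided alpha 0.05; number of readings M = 12 (sessions) or M = 3 (main assessments), both from Section 10.0.

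**Formulas (normal approximation).**
- Average level: variance of one person's mean = 0.35² × VF, where VF = (1/M²) × the sum of ρ^|i−j| over all pairs of readings i, j.
- Change: SD = 0.35 × √(2(1−r)).
- Baseline-adjusted: SD = 0.35 × √(1−r²).
- Detectable difference = (1.960 + 0.842) × SD × √(1/n₁ + 1/n₂).

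**Step 1: reproduce 0.20 at 0.45.**
- Average over 12 sessions, 10 vs 10: VF = 0.199, SD = 0.35 × √0.199 = 0.156. Detectable difference = 2.802 × 0.156 × √0.2 = 0.196; power for 0.20 is 82%.
- Average over 3 visits, 40 vs 20: VF = 0.578, SD = 0.266. Detectable difference = 2.802 × 0.266 × √0.075 = 0.204; power 78%.
- Average over 3 visits, 10 vs 10: 0.333; power 39%.
- Single reading, 10 vs 10: 0.439.
- Pre-to-post change: SD = 0.35 × √1.10 = 0.367. Detectable difference 0.460 (10 vs 10) or 0.282 (40 vs 20).
- Baseline-adjusted: 0.392 (10 vs 10) or 0.240 (40 vs 20).

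Only the first two match the plan's figure, and both are differences in average level. The first also matches the stated 10 per group.

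**Step 2: raise the correlation. Power for a difference of 0.20:**

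| Quantity | Groups | 0.45 | 0.80 | 0.90 |
|---|---|---|---|---|
| Average, 12 sessions, AR(1) | 10 vs 10 | 82% | 45% | 34% |
| Average, 3 visits, AR(1) | 40 vs 20 | 78% | 63% | 59% |
| Pre-to-post change | 10 vs 10 | 23% | 52% | 82% |
| Pre-to-post change | 40 vs 20 | 51% | 91% | 99.7% |
| Baseline-adjusted | 10 vs 10 | 30% | 57% | 83% |
| Baseline-adjusted | 40 vs 20 | 65% | 94% | 99.8% |

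The first two rows fall as correlation rises and the other four rise. In the 0.45 column, no row both reaches about 80% and gains from a higher correlation. Using the t distribution in place of the normal lowers most entries by about 1 to 4 points and leaves the pattern unchanged.

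**The case against.** The strongest reply is that the result depends on inputs the plan does not state. With other numbers of readings or group splits, 80% power for an average-level difference of 0.20 survives a higher AR(1) correlation: up to 0.70 for 24 readings with 10 vs 10, and up to 0.84 for 12 readings with 40 vs 20. That is correct. But at the stated 0.45 those two configurations would detect about 0.14 and 0.12, so they are not the calculation the plan reports.

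The second reply is that the remark about additional power is hedged, and follows a session-by-session model with time interactions. For change or baseline-adjusted contrasts it is right: change at r = 0.90 with 10 vs 10 detects 0.196. This stands, and is why the sentence should be limited in scope and not deleted.

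Third, the cited ICC is test-retest reliability. It is not the correlation across four weeks of training, and it need not equal the pilot model's AR(1) parameter. This also stands. The ICC is consistent with a high correlation but does not refute 0.45.

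A reader might infer that the calculation treats one person's readings as almost independent. It does not. Neighbouring readings correlate 0.45, and 12 readings count as about 5 independent ones (1/0.199); full independence would have given 0.127, not 0.196.

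**Conclusion.** The point holds, as a mismatch between the power figure and the aim. At the stated SD and AR(1) 0.45, the 0.20 is reproduced only as a time-averaged difference in level, and a high correlation reduces power for that quantity from 82% to 34% (10 vs 10, 12 sessions) or from 78% to 59% (40 vs 20, 3 visits). For pre-to-post improvement a high correlation helps, but at 0.45 power for 0.20 is 23% or 51%. The stated figure and the expected gain therefore cannot both be claimed for one contrast among those checked.

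A reader might go on to infer that the trial is underpowered for Aim 1. The documents do not support that. If the pre-to-post correlation is near 0.90, change or baseline-adjusted SSWS would detect 0.20 or less even with 10 vs 10; for the pooled 40 vs 20 comparison, the baseline-adjusted detectable difference is already 0.192 at a correlation of 0.70.

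These results assume two-sided 5% with no Bonferroni division, M of 12 or 3, a constant SD of 0.35, and 0.20 and 0.35 on the same scale. If that scale is log, 0.20 is a ratio of e^0.20 = 1.22 and not 0.20 m/s.

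**What to change.** 1. Recompute the detectable difference for baseline-adjusted SSWS (or change in SSWS) at the post-training visit, using the pilot's pre-to-post correlation. State the contrast to be tested with its group sizes, the alpha and sidedness, and whether the scale is log or m/s.
2. Show the result for correlations from 0.45 to 0.95, which covers both of the plan's statements. On the assumptions above, the baseline-adjusted figure runs from 0.392 to 0.137 for 10 vs 10 and from 0.240 to 0.084 for 40 vs 20. Replace the present 0.20 sentence with the restated figure.
3. Limit the additional-power sentence to change or baseline-adjusted contrasts.
4. Label the covariate and sub-type analyses exploratory.

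The cost is one recalculation and a few sentences, with no change in enrolment. The restated figure may be less or more favourable than 0.20, depending on the pilot correlation.

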
[name] will be the unblinded statistician who will track the trial to ensure adverse events are not disproportionately harmful to any one group of participants. After every adverse event, a report will be prepared by [name] and shared with the team and the MUSC IRB. All serious adverse events will be analyzed by the investigative team and the MUSC Institutional Review Board. Serious adverse events are defined as 1) being unexpected; 2) related to a subject's participation in research; and 3) that subjects are at greater risk of harm than was previously recognized. If > than 10% in each cell have a serious adverse event, we will evaluate the circumstances and decide if the event was caused by a particular treatment. If a majority of team or the IRB decides that the adverse event was related to intervention, subsequent randomizations will be stopped.

12.0 Provisions to Monitor the Data to Ensure the Safety of Subjects (if applicable)

Informed consent will be obtained by the on-site R&D IRB approved VA research staff (i.e. research therapist, research assistant, investigator, coordinator, or other associated trained staff) in a private room located at the Center for Rehabilitation Research in Neurological Conditions (CNNRC), Dept. of Health Sciences and Research, MUSC, [name].2nd Floor, Room C214 and 213 (designated VA space through MOU between MUSC and VA).

All hard copies of signed consent forms and associated data (intake form) will be stored in a locked office located on the 2nd floor, Room C213, north wall, in a badge access and secure building at the Medical University of South Carolina ([name], designated VA space through a Memorandum of Understanding between MUSC and VA).

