13.0 Risks to Subjects

Potential Risks: There are no significant risks to the subjects in the proposed training methods. The risks to individuals participating in this study are no greater than the risks when providing conventional physical rehabilitation services to an individual after stroke. The same precautions and safety guidelines will be taken that are provided in patient care in rehabilitation settings. The rehabilitation program should not present a risk for the patient but could result in muscle soreness and/or joint stiffness but these symptoms should not persist more than a few days. There is a minimal risk for muscle strains during the testing and training. The locomotor assessments used in the proposed study are routine, clinical assessments of gait used in physical therapy clinics and rehabilitation facilities. The GAITRite system has been used to assess walking performance with no adverse reactions or report of discomfort. The experimental protocol to be used in this portion of the proposal involves minimal risk, and is considered standard clinical practice. During all treadmill walking trials and training sessions, a safety harness will be worn and a trained staff member will be present to provide assistance in the event of loss of balance. During training, individuals will be allowed to use a small amount of body weight support ($\leq 20\%$ of body weight) to facilitate independent walking. The harness will be designed to eliminate the consequences of falling as the device “catches” the subject should they trip or stumble. The presence of this device affords comfort and diminishes the “fear of falling” in subjects.

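### The only numerical group-level harm trigger cannot count severe events judged unrelated to participation, and Sections 11.0 and 13.0 attach different stops to it

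*Combined protocol and SAP*

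**What the plan says.** The group-level safety rule appears twice, in Section 11.0 (Data Management, after the statistical approach) and in Section 13.0 (Risks to Subjects). Section 12.0, whose title concerns safety monitoring, covers only consent and the storage of forms.

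Both versions use the same definition. It begins "Serious adverse events are defined as 1) being unexpected; 2) related to a" subject's participation in the research, and its third condition, joined by *and*, is "that subjects are at greater risk of harm than was previously recognized". Neither version mentions death, threat to life, hospitalization or disability.

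Both then set the same threshold, in Section 11.0 worded "If > than 10% in each cell have a serious adverse event, we will evaluate the circumstances". Crossing it leads the team to "decide if the event was caused by a particular treatment".

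The consequences differ. Section 11.0 says: "If a majority of team or the IRB decides that the adverse event was related to intervention, subsequent randomizations will be stopped". Section 13.0, after the same trigger and the same judgement, has a named role stop allocating the affected patient profile to the affected group.

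Two safeguards sit outside the threshold. An unblinded statistician will "track the trial to ensure adverse events are not disproportionately harmful to any one group of participants". Section 11.0 also provides for individual reports: "After every adverse event, a report will be prepared by" that statistician and shared with the team and the IRB.

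**The concern.** The rule asks about cause twice, and the first answer can close off the second. An event must already be judged related to participation before it is counted. Only when enough have been counted does anyone ask whether a particular treatment caused them. An event unrelated to participation cannot have been caused by the training, so a negative first answer settles the later question before the evaluation meant to examine it.

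In cells of 10 to 12 a single hospitalization in a person with chronic stroke is hard to attribute. Accumulation in one cell is one of the few group-level signals available, and the rule removes it by filtering event by event.

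Expectedness probably filters little. The foreseeable effects in Section 13.0 are muscle strain and training that "could result in muscle soreness and/or joint stiffness but these symptoms should not persist more than a few days", so a death or hospitalization would rarely be expected. Relatedness does most of the excluding.

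The second problem is operational. If a stop is reached, whoever runs randomization holds two instructions of different scope.

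**Working it through.** The plan gives no operating characteristics for this rule, so there is no figure of its own to reproduce. The defect follows from the text; the arithmetic only sizes it.

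**Inputs.** Six Pp-by-training cells. There are 60/6 = 10 per cell as analysed and 72/6 = 12 as recruited (Sections 6.0 and 11.0). The threshold is more than 10%. The documents give no event rates, so every rate below is an assumption.

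**Threshold as a count.** 1/10 = 10%, which does not exceed 10%, and 1/12 = 8.3%. 2/10 = 20% and 2/12 = 16.7%. A full cell therefore triggers at 2 participants. The plan does not say whether the denominator is the planned or the current cell size.

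**Is it the only numerical group rule?** The blood pressure, heart rate and exertion limits in Sections 3.0 and 13.0 end or pause one person's session. They are not group rules.

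**What the filter does, with no rate assumed.** Take three participants hospitalized in one cell, each judged unrelated.
- Present rule: 0 counted, no trigger.
- Outcome-based counting: 3/10 = 30% or 3/12 = 25%, trigger.

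**How far such a cluster points to a cell,** with equal cells and no effect of training or profile:
- Exactly three affected in the trial, all in one cell: 6·C(10,3)/C(60,3) = 720/34,220 = 2.1%; with 12 per cell, 6·C(12,3)/C(72,3) = 1,320/59,640 = 2.2%.
- Exactly two affected, both in one cell: 6·C(10,2)/C(60,2) = 270/1,770 = 15.3%; with 12 per cell, 6·C(12,2)/C(72,2) = 396/2,556 = 15.5%.

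Three together would be notable. Two together, the actual trigger, is weak evidence and justifies a review but not a stop.

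**Reviews from background events under outcome-based counting.** Per cell, q = P(X ≥ 2) for a binomial with n = 10 or 12; for any of six cells, 1 − (1 − q)^6.

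| Assumed rate | q (n = 10 / 12) | Any of six cells |
|---|---|---|
| 1% | 0.0043 / 0.0062 | 0.025 / 0.036 |
| 2% | 0.0162 / 0.0231 | 0.093 / 0.131 |
| 5% | 0.0861 / 0.1184 | 0.418 / 0.530 |

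**Scope of the stop.** Section 11.0 read literally closes 6 of 6 cells. If it is read as limited to the implicated training, it closes that training for both profiles, 2 of 6. Section 13.0 closes 1 of 6. No reading of Section 11.0's own wording gives Section 13.0's scope.

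**The case against.** The strongest reply is that oversight does not depend on this number. Every adverse event goes to the team and the IRB, and an unblinded statistician watches for imbalance. That stands. A reader might infer that severe events judged unrelated go unreported or unwatched, and the documents do not support that. The gap is that no count obliges anyone to act on what is seen.

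A reader might also infer a quantity of missed treatment harm. At an assumed 10% rate of severe events, the chance that a full cell triggers is 0.26 to 0.34 if all count and 0.09 to 0.12 if half are set aside as unrelated. No treatment-caused rate enters that comparison. If the excluded events really are unrelated, excluding them loses nothing, and the same probabilities describe false triggers: 0.09 to 0.12 is also the per-cell chance at a 5% background rate. These figures should not be presented as missed harm.

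Third, the two causality questions differ. Participation includes testing as well as training, so a positive first answer leaves the second open. The plan also does not bar revising a relatedness judgement once a cluster appears. Both points are fair, but a negative first answer still carries over, and nothing requires revision.

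Fourth, replacing the present definition with an outcome-only one would lose something. An unexpected, training-related injury without hospitalization can count now if it shows new risk, and it would then drop out. This is right, and it determines the form of the fix.

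On the stop, Section 13.0 is the more specific text and could be taken to govern. It also refers to a fuller description in other sections, which may lie outside this document. The reading is reasonable, but nothing here states it. The each-cell wording of the threshold, read literally, would require all six cells to exceed 10%. It probably means any one cell and needs only rewording.

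**Conclusion.** The point holds and should be fixed. As written, the one numerical group-level trigger cannot register deaths or hospitalizations individually judged unrelated, whatever their number or clustering, and the stop that follows it has two scopes (6 or 2 of 6 cells against 1 of 6). Both conclusions rest on the text alone and need no assumed rate. The consequence is limited by the reporting of every adverse event and by unblinded tracking. This is an error in the rule, not an absence of safety oversight, and it is not evidence that harm would be missed at any particular rate. The clustering figures assume equal full cells and no effect; the review-burden figures also assume independent events and the rates shown.

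**What to change.** Make the same changes in Sections 11.0 and 13.0.

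1. Count toward the trigger any participant with a death, life-threatening event, hospitalization or lasting disability, regardless of expectedness or relatedness. Also count any participant with an event meeting the present three criteria. Leave causality to the evaluation step the rule already has.
2. Word the trigger as at least 2 participants in any one of the six Pp-by-training cells. This matches more than 10% of a full cell of 10 or 12 and removes the each-cell ambiguity. Continue individual review of single serious events by the team and IRB.
3. State one action: Section 13.0's cell-specific stop, with the team or IRB able to widen it to the whole training arm.

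The cost is protocol wording and some extra reviews. From outcome-based events alone, background would prompt at least one review in about 3 to 4% of trials at an assumed 1% rate, 9 to 13% at 2% and 42 to 53% at 5%. When exactly two participants have unrelated events, they share a cell by chance about 15% of the time. Each trigger leads to a review, not an automatic stop.
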